3.4. Duration of Treatment

The HIV treatment duration is from the Day 1 visit until the last study visit at the Post-HCV Treatment Week 12. The HCV treatment duration is 12 weeks. Screening assessments will be completed within 42 days of the Day 1 visit.

All subjects will complete the following study visits: Screening, Day 1, Weeks 4, 6 (laboratory visit only), 8 (start of HCV treatment), 12, 16, and 20 (end of HCV treatment), and post-HCV treatment visits 4 and 12 weeks after the last LDV/SOF dose.

Subjects who complete the study through the last study visit at the Post-HCV Treatment Week 12 visit will be required to return to the clinic 30 days after the completion of the study treatment for a 30-Day Follow-Up visit.

- a Following the Day 1 visit, subjects will return for study visits at Weeks 4, 6 (laboratory visit only), 8, 12, 16, 20, and Post-HCV Treatment 4 and 12 weeks after the last LDV/SOF dose.
- b Part 1: subjects are randomized to either E/C/F/TAF FDC or F/R/TAF FDC on Day 1 and maintain HIV treatment to the Week 8 visit.
- c Part 2: At Week 8, once HIV-1 RNA suppression (< 50 copies/mL) is confirmed (based on the Week 6 HIV-1 RNA value), subjects will start on LDV/SOF FDC for 12 weeks (until Week 20) while maintaining their HIV treatment. At Week 20, LDV/SOF FDC will be discontinued while continuing HIV treatment. Subjects will continue in the study for another 12 weeks to determine SVR4 (4 weeks post-HCV treatment) and SVR12 (12 weeks post-HCV treatment).

- d Subjects who complete the study through the Post-HCV Treatment Week 12 visit will be required to return to the clinic 30 days after the completion of the study treatment for a 30-Day Follow-Up Visit.
- e At the Day 1 visit, subjects will switch to either E/C/F/TAF FDC or F/R/TAF FDC and continue on HIV treatment until the last study visit at the Post-HCV Treatment Week 12 visit.

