6.4.2. HIV Treatment and Post-HCV Treatment Assessments (Post-HCV Treatment Weeks 4 and 12)

The following evaluations are to be completed at the end of 4 and 12 weeks after completion of HCV treatment (Post-HCV Treatment Weeks 4 and 12 visits, respectively) and should be timed from the date of last administration of the HCV treatment. The Post-HCV Treatment Week 4 visit is to be completed \pm 2 days, and the Post-HCV Treatment Week 12 visit is to be completed within \pm 4 days; however, unless notified by Gilead Sciences, the Post-HCV Treatment Week 4 and 12 should be completed within 2 and 4 days of the protocol-specified visit date, respectively.

All subjects must complete the Post-HCV Treatment Weeks 4 and 12 visits. The end of study will occur at the Post-HCV Treatment Week 12 visit.

The following assessments are to be completed:

- Review AEs and changes in concomitant medications
- Complete physical examination (**Post-HCV Treatment Week 12 only**) (urogenital/anorectal exams will be performed at the discretion of the Investigator)
- Perform symptom-directed physical examination as needed
- Obtain vital signs, including weight
- Obtain urine samples for the following laboratory analyses:
 - Urinalysis and urine chemistry
 - Urine pregnancy test (females of childbearing potential only); positive urine pregnancy tests will be confirmed with a serum test. If the serum test is positive, the subject will be discontinued.
 - Renal tubular function assessments (Post-HCV Treatment Week 12 only)
 - Urine sample storage for possible additional clinical testing
- Obtain blood samples for the following laboratory analyses:
 - Chemistry profile
 - Hematology profile
 - Coagulation assessments
 - Metabolic assessments (Post-HCV Treatment Week 12 only)

- CD4+ cell count
- Plasma HIV-1 RNA
- Plasma HCV RNA
- Serum bone safety assessments (Post-HCV Treatment Week 12 only)
- Platelet and coagulation function assessments (Post-HCV Treatment Week 12 only)
- Inflammation assessments (Post-HCV Treatment Week 12 only)
- Plasma storage samples for virology, safety, and/or PK testing
- Serum storage sample for possible additional clinical testing

- PPD

- Obtain estimated glomerular filtration rate according to the Cockcroft-Gault formula (see Section 4.2 for details)
- Complete questionnaires (Post-HCV Treatment Week 12 only): subject is to read questionnaire by her/himself and write/mark answers directly onto the questionnaires.
 - VAS for HIV adherence

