- Complete physical examination (urogenital/anorectal exams will be performed at the discretion of the Investigator)
- Obtain vital signs, including weight
- Obtain 12-lead ECG (performed supine)
- Obtain urine samples for the following laboratory analyses:
 - Urinalysis and urine chemistry
 - Urine pregnancy test (females of childbearing potential only); positive urine pregnancy tests will be confirmed with a serum test.
 - Urine sample storage for possible additional clinical testing
- Obtain blood samples for the following laboratory analyses:
 - Chemistry profile
 - Hematology profile
 - CD4+ cell count
 - Plasma HIV-1 RNA
 - Plasma HCV RNA
 - Plasma storage samples for virology, safety, and/or PK testing

• Obtain estimated glomerular filtration rate according to the Cockcroft-Gault formula (see Section 4.2 for details)

- Complete questionnaires: subject is to read questionnaire by her/himself and write/mark answers directly onto the questionnaires.
 - VAS for HIV adherence
 - HIVTSQc Change version
 - SF-36
 - FACIT-F
 - CLDQ-HCV
 - WPAI: Hepatitis C
- HIV-1 genotype/phenotype resistance testing for subjects with unconfirmed virologic rebound with HIV-1 RNA value ≥ 400 copies/mL.
- Perform study drug accountability:
 - For subjects that **discontinue during Part 1 of the study**, perform study drug accountability on HIV study drugs.
 - For subjects that **discontinue during Part 2 of the study**, perform study drug accountability for HIV and HCV study drugs.
 - If the subject discontinues HCV study drug and is staying on HIV study drug, dispense HIV study drug until the last study visit.
 - If the subject discontinues HIV study drug, HCV study drug will be dispensed at the scheduled visits as described in Section 6.4.1

6.5.2. **30-Day Follow-Up Visit**

Subjects who complete the study through the Post-HCV Treatment Week 12 visit will be required to return to the clinic 30 days after the completion of study for the 30-Day Follow-Up visit.

Subjects who permanently discontinue HIV study drug in Part 1 of the study will be asked to return to the clinic after the completion of the ESDD visit for a 30-Day Follow-Up visit.

 $A \pm 6$ days window may be used to schedule this visit. The following evaluations are to be completed at this visit:

- Review of AEs and changes in concomitant medications
- Perform symptom-directed physical examination

- Obtain vital signs measurement, including weight

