- Obtain urine samples for the following laboratory analyses:
 - Urinalysis and urine chemistry
 - Urine pregnancy test (females of childbearing potential only); positive urine pregnancy tests will be confirmed with a serum test.
- Obtain blood samples for the following laboratory analyses:
 - Chemistry profile
 - Hematology profile
 - CD4+ cell count
 - Plasma HIV-1 RNA
 - Plasma HCV RNA

At the 30-Day Follow-Up Visit, any evaluations showing abnormal results indicating that there is a reasonable possibility of a causal relationship with the study drug will be repeated weekly (or as often as deemed prudent by the Investigator) until the abnormality is resolved, returns to baseline, or is otherwise explained.

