1.2.5. Schedule of Assessments

After obtaining informed consent, screening assessments will be completed within 42 days prior to the Day 1 visit, including physical examination, height, weight, vital signs, medical history, 12-lead electrocardiogram (ECG), screening procedure-related adverse events (AEs), concomitant medications (CMs), clinical laboratory tests (including hematology, coagulation, and chemistry, and), urinalysis, plasma concentrations of HIV-1 RNA and HCV RNA, serology (HIV, HCV, hepatitis B virus [HBV]), historical HIV resistance (if not available; HIV DNA archive genotype), HCV genotyping, IL28B genotyping, cirrhosis determination, serum β -hCG (females of child bearing potential only).

On treatment assessment will occure as follows:

- **Part 1:** Switch to F/TAF-based ARV regimen:
 - Day 1 and Weeks 4, 6 (HIV-1 RNA only), and 8
- Part 2: LDV/SOF treatment and follow-up
 - At first dose of LDV/SOF at Week 8, and at Weeks 12, 16, and 20 (ie, 4, 8, and 12 weeks after start of LDV/SOF) and follow up at 4 and 12 weeks post LDV/SOF treatment.

On treatment and post HCV treatment assessments will include HIV-1 RNA and HCV RNA plasma concentrations, CD4 cell count, adherence to study drug dosing (including pill count), physical examination, weight, vital signs, clinical laboratory tests, urine pregnancy tests (females of child bearing potential only), monitoring of AEs and CMs, and patient-reported quality-of-life (QoL) assessments.

Fasting lipid profile measurements and fasting glucose will be performed at Day 1, Weeks 8 and 20, and at Post HCV Treatment Week 12. Lipids will include total cholesterol (TC), high density lipoproteins (HDL), low density lipoproteins (LDL), non-HDL cholesterol, triglycerides (TGs) and cholesterol ratios.

Post HIV treatment assessments (30 days after the last dose of HIV study drug) will include HCV RNA, HIV RNA, CD4 count, physical examination (including vital signs and weight), 12-lead ECG, clinical laboratory tests (including hematology, chemistry, and urinalysis, urine pregnancy tests (females of childbearing potential only), and AEs and CMs.

Plasma samples for HCV RNA and HIV-1 RNA will be collected at Day 1 and every visit thereafter (no HCV RNA at Weeks 4 and 6).

Calculated creatinine clearance, hematology, serum chemistry, and urinalysis tests will be performed at all study visits and early study drug discontinuation (ESDD) visits as applicable.

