3.8.2.2. Part 2 Analysis Windows for HCV RNA and Part 2 Safety Data

For clearity of by-visit summary, the visit IDs of Part 2 analysis windows corresponding to the protocol planned visits Week 8, Week 12, Week 16, and Week 20 are renamed to Part 2 Baseline, Week 4, Week 8, and Week 12 respectively, as counted starting from Part 2 Day 1. Data of HCV RNA and safety assessments collected up to the last dose date of LDV/SOF + 3 days are considered to be **on-LDV/SOF data**. The Part 2 analysis windows for on-LDV/SOF HCV RNA, weight, vital signs, metabolic assessments, laboratory tests, and bone and renal biomarkers are provided in Table 3-4.

Table 3-4. Part 2 Analysis Windows^a for On LDV/SOF Data from HCV RNA, Weight, Vital Signs, Metabolic Assessments, and Laboratory Tests

Visit ID	Nominal LDV/SOF Day ^b	HCV RNA, Laboratory Tests, Weight, and Vital Signs	Fasting Glucose and Lipid Panel	Bone and Renal Biomarkers
Part 2 Baseline		≤1	≤ 1	≤ 1
Week 4	28	[2, 42]	N/A	[2, 56]
Week 8	56	[43, 70]	IN/A	N/A
Week 12	84	≥71	≥ 2	≥ 57

- a This analysis window will be applied to data collected up to the last dose date of LDV/SOF + 3 days;
- b This analysis window will be calculated from Part 2 Days defined in Section 3.8.1.

The Part 2 analysis windows for post LDV/SOF data from HCV RNA, weight, vital signs, metabolic assessments, laboratory tests, and bone and renal biomarkers is the same as the study analysis windows specified in Table 3-3.

3.8.3. Selection of Data in the Event of Multiple Records in an Analysis Visit Window

Depending on the statistical analysis method, single values may be required for each analysis window. For example, change from baseline by visit usually requires a single value, whereas a time-to-event analysis would not require one value per analysis window. When a single value is needed, the following rule(s) will be used:

If multiple nonmissing numeric observations exist in a window, records will be chosen as follows:

- For both Study and Part 2 baselines, the last available record on or prior to the dates of the first dose dates of HIV and HCV study drugs, respectively, will be selected. If there are multiple records with the same time or no time recorded on the same day, average (arithmetic mean) will be used for the baseline value, except for HIV-1 RNA (see below).
- For postbaseline visits:
 - For CD4+ cell count, CD4%, and post LDV/SOF HCV RNA, the record(s) collected on the lastest day in the window will be selected for anlaysis.

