 - For other numeric observations (eg, except HIV-1 RNA, HCV RNA, CD4+ cell count, and CD4%), the record(s) collected on the day closest to the nominal day for that visit will be selected. If there are 2 days equidistant from the nominal day, the later day will be selected.
 - For any numeric observations except HIV-1 RNA, If there is more than 1 record on the selected day, the average (arithmetic mean) will be taken.
- For baseline and postbaseline HIV-1 RNA, the latest (considering both date and time) record(s) in the window will be selected. If both "HIV RNA Taqman 2.0" and "HIV RNA Repeat" (ie, the HIV-1 RNA result obtained from an additional aliquot of the original sample) are available with the same collection time, the results from the "HIV RNA Repeat" will be selected for analysis purposes; otherwise, if there are multiple "HIV RNA Taqman 2.0" records with the same collection time, the geometric mean will be taken for analysis purposes.

If multiple valid nonmissing categorical observations exist in an analysis window, records will be selected as follows:

- For baselines, the last available record on or prior to the first dose dates of study drugs will be selected. If there are multiple records with the same time or no time recorded on the same day, the value with the lowest severity will be selected (eg, normal will be selected over abnormal).
- For postbaseline visits, follow the same rules described above for postbaseline numeric observations, except that if there are multiple records with the same time or no time recorded on the same day, the value with the highest severity will be selected (eg, abnormal will be selected over normal).

PROs do not apply to above since no analysis window is assigned. For each nominal visit, if multiple observations exist, records will be set to missing.

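### The latest-record rule for post-treatment HCV RNA makes the 30-Day Follow-Up sample (about Week 16), not the scheduled Week 12 sample, the SVR12 result for completers with both samples

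*SAP*

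**What the plan says.** **Endpoint.** SAP 6.1.1 defines SVR12 as HCV RNA below LLOQ 12 weeks after LDV/SOF is stopped, in the HCV FAS.

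**Window.** SAP Table 3-3 gives FU-12 a nominal FU Day of 84 and an HCV RNA window of [70, 146]. FU Day is the collection date minus the last LDV/SOF dose date. Footnote b to that table identifies FU-12 with the post-HCV Treatment Week 12 visit.

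**Selection.** Where several records fall in one window, SAP 3.8.3 states that for "post LDV/SOF HCV RNA, the record(s) collected on the lastest day in the window will be selected". The closest-to-nominal-day rule in the next bullet leaves HCV RNA out: "For other numeric observations (eg, except HIV-1 RNA, HCV RNA, CD4+ cell count, and CD4". Categorical results are handled alike: "For postbaseline visits, follow the same rules described above for postbaseline numeric observations".

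**Visits.** Protocol 6.4.2 says the post-HCV visits "should be timed from the date of last administration of the HCV treatment", with ±4 days at Week 12. Protocol 3.4 says that subjects who complete the study are "required to return to the clinic 30 days after the completion of the study treatment for a 30-Day Follow-Up visit". Protocol 6.5.2 allows ±6 days for it ("days window may be used to schedule this visit") and lists "Plasma HCV RNA" among its blood tests. SAP 1.2.5 agrees: "Post HIV treatment assessments (30 days after the last dose of HIV study drug) will include HCV RNA".

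**The concern.** Two scheduled HCV RNA samples about a month apart fall in one analysis window, and the tie-break picks the later one. The number reported as SVR12 would then be a response rate at about Week 16 for most completers, and a Week 12 rate only for those without the later sample. The primary endpoint as programmed would differ from the primary endpoint as defined. The SVR12 subgroup displays (SAP 6.1.4) and the SVR12 virologic-failure table (SAP 6.3.2.4) rest on the same FU-12 data.

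Nothing in the visible text removes the later sample. SAP 3.1.2.2 keeps all HCV efficacy data collected after the last LDV/SOF dose unless otherwise specified. SAP 2.2 runs the SVR12 analysis after the 30-Day Follow-Up, so its results will be in the dataset. Where the SAP wants that visit left out, it says so by name: SAP 3.8.1 for imputing last dose dates, and SAP 4.2.1 for duration of exposure.

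**Working it through.** **The plan's own figure.** 12 weeks × 7 = FU Day 84, which matches the nominal day in Table 3-3.

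**Visits timed from the last LDV/SOF dose (Protocol 6.4.2).**
- Week 12 sample: 84 ± 4 = FU Day 80 to 88.
- 30-Day Follow-Up: for completers, HIV study drug ends at the Post-HCV Week 12 visit (Protocol 3.4). Counting 30 days from the end of treatment or from the end of the study therefore gives the same date. Earliest 80 + 30 − 6 = 104; nominal 84 + 30 = 114; latest 88 + 30 + 6 = 124.
- In weeks: 104/7 = 14.9, 114/7 = 16.3, 124/7 = 17.7.
- Both ranges lie inside [70, 146].

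The follow-up sample is always at least 24 days after the Week 12 sample. In all 9 × 13 = 117 combinations of permitted days, the latest-record rule selects the follow-up sample.

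**Visits timed from Day 1 (footnote c to the study procedures table, Protocol Appendix 2 and SAP Appendix 1).** Assume LDV/SOF starts on Study Day 56 ± 2 and runs 84 days.
- Last dose: 54 + 83 = 137 to 58 + 83 = 141.
- Week 12 visit: 224 ± 4 = Study Day 220 to 228.
- Week 12 sample: 220 − 141 = 79 to 228 − 137 = FU Day 91.
- 30-Day Follow-Up: 79 + 24 = 103 to 91 + 36 = FU Day 127.

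Both ranges are again inside the window, and the result is the same.

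**When the problem would not arise.** The follow-up sample leaves the window only if the Week 12 visit is later than 146 − 30 = FU Day 116, or later than 146 − 36 = FU Day 110 when the follow-up is itself 6 days late. Both are far outside the protocol's visit window.

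**Comparison with the closest-day rule.** With visits timed from the last dose, the Week 12 sample is at most 4 days from Day 84 and the follow-up sample at least 20. With visits timed from Day 1, the distances are at most 7 and at least 19. Closest-to-Day-84 therefore picks the Week 12 sample every time.

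**SVR4.** For subjects on schedule, the 30-Day Follow-Up falls well beyond the FU-4 window of [21, 69], so SVR4 is not affected.

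**What one discordant subject would do.** If all 120 enter the HCV FAS, one changed status moves the pooled rate by 1/120 = 0.8 percentage points and a group of 60 by 1/60 = 1.7 points. Whether that changes a conclusion depends on which primary test applies, because the two documents differ:
- Protocol 8.4.1 (pooled, two-sided 0.05): 113/120 is needed (p = 0.035; 112/120 gives p = 0.090). One loss flips the result only from exactly 113, one gain only from exactly 112. At a true 96% these counts have probabilities 9.7% and 5.7%.
- SAP 6.1.2 (each group, 0.025): 59/60 is needed (58/60 gives p = 0.044). One loss flips a group only from 59, one gain only from 58. At a true 96% these have probabilities 21.6% and 26.5%.

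These probabilities describe how often a count would sit at the edge. They do not say how often a discordant pair would occur.

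**The case against.** The rule is prespecified, names post-LDV/SOF HCV RNA explicitly and treats both arms alike. An analysis window is the normal way to put a 12-week definition into practice, and a wide one usefully rescues late or missed visits. A sponsor could prefer the latest sample because it captures late relapse, and a loss of response after Week 12 lowers the count, so it cannot manufacture a success. Footnote b to Table 3-3 suggests that the scheduled visit was intended all along, which points to a drafting slip.

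Much of this stands. The window can stay, and there is no sign of an intended change of endpoint. But windows are assigned by day (SAP 3.8.2), so the footnote does not override the selection rule. The 30-Day Follow-Up is a separate scheduled visit, not a late Week 12 visit. The conservatism argument covers one direction only: a quantifiable Week 12 result followed by one below LLOQ would be counted as a success.

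A reader might infer that the rule costs a definite amount of power, or that it biases SVR12 in a known direction. The documents support neither, since they give no rate at which the two samples disagree in either direction. Power losses worked out from assumed rates for the protocol's pooled test would not describe the SAP's per-group test either. With 60 per group and a true rate of 96%, that test has only 30.2% power before any discordance.

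**Conclusion.** Wrong as written, and it should be fixed. For every on-schedule completer with both samples, the stated rule selects a sample taken about 15 to 18 weeks after LDV/SOF as the 12-week primary endpoint. This conflicts with SAP 6.1.1 and with footnote b to Table 3-3. It follows from the visit schedule alone, under either way of timing the visits, and does not depend on sample size or on any response rate.

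The size of the effect on the SVR12 rate, on power or on the conclusion is unknown. A subject's status changes only if the two samples disagree. Loss of response after Week 12 would lower the count and the reverse would raise it. The finding is that the endpoint's derivation does not match its definition; it is not that the result is biased by a stated amount.

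The conclusion assumes that visits occur within their permitted windows, that both samples are taken, and that no unseen programming instruction excludes the 30-Day Follow-Up.

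**What to change.** In SAP 3.8.3 and Table 3-3, select the FU-12 HCV RNA by nominal visit:

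- Use the Post-HCV Treatment Week 12 visit sample, or its retest, whenever one exists.
- Use the 30-Day Follow-Up sample, if within [70, 146], only when there is no Week 12 sample.
- List the 30-Day Follow-Up HCV RNA separately, so that any late change remains visible.

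Two places in 3.8.3 need editing: the bullet that sets the latest-day rule for post-LDV/SOF HCV RNA, and the next bullet, which excepts HCV RNA from the closest-day rule.

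A fixed cut-off such as FU Day 104 should not be used. With visits timed from Day 1, the follow-up can fall on FU Day 103 and would still be picked up by a latest-record rule.

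Taking the record closest to FU Day 84 is an acceptable alternative. Its small drawback is that a later unscheduled retest would not replace the scheduled value.

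The cost is one or two sentences of SAP text and a small programming change before database finalization. No new data are needed.

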4. SUBJECT DISPOSITION

4.1. Subject Enrollment and Disposition

4.1.1. Subject Enrollment

The number and percentage of subjects randomized at each country and by each investigator will be summarized by treatment group (E/C/F/TAF + LDV/SOF or F/R/TAF + LDV/SOF) and overall using the Safety Analysis Set. Similarly, the number and percentage of subjects enrolled in the randomization stratum of race (black, non-black) will also be summarized by treatment group and overall, using the Safety Analysis Set.

4.1.2. Disposition of Subjects

The summary of subject disposition will be provided by treatment group and overall. This summary will present the number and/or percentage of subjects screened, screen failure subjects who are not randomized, subjects who met all eligibility criteria and are not randomized, subjects randomized, subjects randomized but not treated, subjects in the Safety Analysis Set and Part 2 Safety Analysis Set, and subjects in the HIV FAS and HCV FAS.

In addition, the number and percentage of subjects meeting the following criteria will be summarized:

- Prematurely discontinued HIV study drug in Part 1 of the study (with summary of reasons for discontinuing treatment)
- Entered Part 2 of the study by starting LDV/SOF dosing while still on HIV study drug
- Prematurely discontinued LDV/SOF in Part 2 of the study (with summary of reasons for discontinuing treatment)
- Completed LDV/SOF treatment in Part 2 of the study
- Completed HIV study drug in Part 2 of the study
- Prematurely discontinuing HIV study drug in Part 2 of the study (with summary of reasons for discontinuing treatment)
- Completed study including the 12-week-follow-up period for HCV treatment
- Prematurely discontinued from the study including the 12-week-follow-up period for HCV treatment (with summary of reasons for discontinuing the study)

The denominator for the percentage of subjects in each category will be the number of subjects in the Safety Analysis Set.

No inferential statistics will be generated. A data listing of reasons for premature study drug (E/C/F/TAF, F/R/TAF, LDV/SOF) discontinuation will be provided. A figure of disposition of subjects will also be provided.

